## 2.1 Primary estimands

The estimand is the precise description of the treatment effect and reflects strategies to address events occurring during the trial conduct which could impact the interpretation of the trial results (e.g., premature discontinuation of treatment).

The primary clinical question of interest is: Do relapsing MS participants who receive ofatumumab treatment mount an immune response to non-live mRNA COVID-19 vaccine?

The justification for the primary estimand is that it will capture whether ofatumumab treated participants generate antibodies to mRNA COVID-19 vaccines.

The primary estimand is described by the following attributes:

- **Population:** Defined through appropriate inclusion/exclusion criteria to reflect the targeted population. Relapsing MS participants subdivided into 6 cohorts. (1) Will receive a full course (two doses) of a COVID-19 mRNA vaccine two weeks prior to starting ofatumumab 20 mg subcutaneous treatment; (2) Will receive a full course (two doses) of a COVID-19 mRNA vaccine after at least 4 weeks of commercial ofatumumab 20 mg subcutaneous treatment (3) Will receive a full course (two doses) of a COVID-19 mRNA vaccine after at least 4 weeks of interferon or glatiramer acetate treatment (4) Completed a full course (two doses) of a COVID-19 mRNA vaccine after at least 4 weeks of commercial ofatumumab 20 mg subcutaneous treatment but has not yet received a COVID-19 mRNA booster (5) Completed a full course (two doses) of a COVID-19 mRNA vaccine after at least 4 weeks of interferon or glatiramer acetate (may or may not have received at least 1 COVID-19 mRNA booster) (6) Completed a full course (two doses) of a COVID-19 mRNA vaccine after at least 4 weeks of commercial ofatumumab 20 mg subcutaneous treatment and received at least 1 additional booster vaccine  $\geq$  14 days prior to Screening.
- **Variable:** Achieving immune response as defined by a positive SARS-CoV-2 qualitative IgG antibody assay  $\geq$  14 days after full course (two doses) vaccination (yes/no)
- **Treatment of interest:** Non-live COVID-19 mRNA vaccine either two weeks prior to ofatumumab start or at least 4 weeks after ofatumumab start or while on interferon or glatiramer acetate
- **Intercurrent event:** Discontinuation of treatment/study, or death
- **Summary measure:** Proportion of participants achieving immune response

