5. Completed a full course (two doses) of a COVID-19 mRNA vaccine at least  $\geq 4$  weeks after start of commercially prescribed ofatumumab for the treatment of RMS
6. Currently on commercially prescribed ofatumumab for  $\geq 4$  weeks for the treatment of RMS
7. Received two dose mRNA COVID-19 vaccine (Pfizer or Moderna vaccine)  $\geq 2$  weeks ago
8. Pre-ofatumumab serologies with Hepatitis B testing not indicative of active or latent infection
9. Total serum immunoglobulin IgG  $\geq 400$  mg/dl at Screening

Patients eligible for inclusion in Cohort 5 of this study must meet **all** of the following criteria:

1. Signed informed consent must be obtained prior to participation in the study
2. Age 18-55 years old at Screening
3. Diagnosis of relapsing MS by 2017 revised McDonald criteria
4. Must be willing to comply with the study schedule
5. Currently on commercially prescribed interferon or glatiramer acetate for  $\geq 4$  weeks for the treatment of RMS
6. Completed a full course (two doses) of a COVID-19 mRNA vaccine after start of glatiramer acetate or interferon
7. Received two dose mRNA COVID-19 vaccine (Pfizer or Moderna vaccine)  $\geq 2$  weeks ago
8. If the patient has received the mRNA booster, then the mRNA booster should be  $\geq 2$  weeks prior to enrollment.
9. Total serum immunoglobulin IgG  $\geq 400$  mg/dl at Screening

Patients eligible for inclusion in Cohort 6 of this study must meet **all** of the following criteria:

1. Signed informed consent must be obtained prior to participation in the study
2. Age 18-55 years old at Screening
3. Diagnosis of relapsing MS by 2017 revised McDonald criteria
4. Must be willing to comply with the study schedule
5. Currently on commercially prescribed ofatumumab for  $\geq 4$  weeks for the treatment of RMS

6. Completed a full course (two doses) of a COVID-19 mRNA vaccine at least  $\geq$  4 weeks after start of commercially prescribed ofatumumab for the treatment of RMS
7. Received two dose mRNA COVID-19 vaccine (Pfizer or Moderna vaccine)  $\geq$  2 weeks ago
8. Pre-ofatumumab serologies with Hepatitis B testing not indicative of active or latent infection
9. Total serum immunoglobulin IgG  $\geq$  400 mg/dl at Screening
10. Has received an mRNA booster  $\geq$  2 weeks prior to enrollment

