### **Special guidance regarding the scheduling of visits for Cohorts 1, 2 and 3**

- The study site will need to perform Vaccine Status Check-ins (make remote contact with participant) to confirm when the 1st and 2nd COVID-19 vaccinations are scheduled in order to schedule Visit 4.
- The date of the 2nd COVID-19 vaccine dose will determine the date of Visit 4 and all other remaining study visits.
- Visits 2 and 3 should always occur prior to administration of the mRNA vaccine.
- The Visit 4 lab samples should be collected 14 days after a participant has received their 2nd COVID-19 vaccine dose.

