## **12 Data analysis and statistical methods**

The analysis will be conducted on all participant data at the time the trial ends. Any data analysis carried out independently by the investigator should be submitted to Novartis prior to publication or presentation.

Categorical variables will be presented as counts and percentages. For continuous variable, mean, standard deviation, minimum, 25th percentile, median, 75th percentile, and maximum will be presented. All summaries will be presented for Cohort 1, Cohorts 2 and 4, Cohorts 3 and 5, and Cohort 6.

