Cohort 2: Relapsing MS participants receiving a full course (2 doses) of a non-live COVID-19 mRNA vaccine ≥4 weeks after ofatumumab start.

Will continue taking their prescribed ofatumumab as per their current dosing schedule.

Cohort 3: Relapsing MS participants receiving a full course (2 doses) of a non-live COVID-19 mRNA vaccine ≥4 weeks after start of prescribed interferon or glatiramer acetate.

Will continue administration of their prescribed interferon or glatiramer acetate as per their current dosing schedule.

Cohort 4: Relapsing MS participants having completed a full course (2 doses) of a non-live COVID-19 mRNA vaccine ≥4 weeks after ofatumumab start.

Will continue taking their prescribed ofatumumab as per their current dosing schedule.

Cohort 5: Relapsing MS participants having completed a full course (2 doses) of a non-live COVID-19 mRNA vaccine ≥4 weeks after glatiramer acetate or interferon start.

Will continue taking their prescribed glatiramer acetate or interferon as per their current dosing schedule.

Cohort 6: Relapsing MS participants having completed a full course (2 doses) of a non-live COVID-19 mRNA vaccine ≥4 weeks after ofatumumab start and having received a booster ≥14 days prior to screening.

Will continue taking their prescribed ofatumumab as per their current dosing schedule.

Study completion

According to the protocol, study completion is defined as when the last participant completes the end of study (EOS) visit. Participants who discontinue study treatment or who decide they do not wish to participate in the study further should NOT be considered withdrawn from the study UNLESS they withdraw their consent. Where possible, they should return for the EOS visit.

Study design schematics for Cohorts 1, 2 and 3 are shown in Figures 1, 2, 3 and 4. Study design schematics for Cohorts 4, 5 and 6 are shown in Figures 5 and 6.

Figure 1 Study Design (Cohort 1, Pfizer)

[figure not shown]

Figure 2 Study Design (Cohort 1, Moderna)

[figure not shown]

Figure 3 Study Design (Cohorts 2 and 3, Pfizer)

[figure not shown]

Figure 4 Study Design (Cohorts 2 and 3, Moderna)

[figure not shown]

Figure 5 Study Design (Cohorts 4, 5 and 6, Pfizer)

[figure not shown]
[figure not shown]

Figure 6 Study Design (Cohorts 4, 5 and 6, Moderna)

Primary analysis time point

The primary analysis time point is Visit 4 for Cohorts 1, 2 and 3, and Visit 2 for Cohorts 4, 5 and 6.

Interim analysis

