2.1 Data analysis general information

The statistical analysis outlined in this SAP will be performed by [REDACTED], a Novartis-designated Contract Research Organization (CRO), using SAS® version 9.4 or higher.

For continuous variables, descriptive statistics will include number of participants (n), mean, standard deviation, minimum, maximum, median and 25th and 75th percentiles. For categorical variables, frequency counts and percentages will be reported. Where appropriate, 2-sided 95% confidence intervals (CIs) for point estimates of the mean or proportion will be provided.

Unless otherwise stated, all data summaries will be presented by **cohort group** (see below) and on all participants in the respective analysis set.

- Cohort 1
- Cohorts 2 and 4 combined
- Cohorts 3 and 5 combined
- Cohort 6

All data will be listed appropriately.

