2.4 Treatments (study treatment, rescue medication, concomitant therapies, compliance)

2.4.1 Study treatment / compliance

Participants in all cohorts must intend to receive or have received both doses of a COVID-19 mRNA vaccine.

The following variables will be summarized descriptively as continuous variables by cohort group unless otherwise specified:

- Time (days) from first dose of ofatumumab to last dose of ofatumumab for Cohort 1 participants
- Time (days) from first dose of earliest MS DMT to:
 - first dose of COVID-19 vaccine
 - primary analysis time point (see [Section 1.1](#))
- Time (days) from first dose of most recent MS DMT to:
 - first dose of COVID-19 vaccine
 - primary analysis time point (see [Section 1.1](#))

MS treatment compliance will be listed by individual cohort and participant.

Study duration

Study duration in days will be calculated as [(date of last contact/EOS – date of Visit 1) + 1] and summarized descriptively as a continuous variable by cohort group.

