Pfizer vaccine:			
Pre-vaccination	Day 1	1	≤1
14 days post-vaccination	Day 36	36	(vaccine day + 1) to 64
70 days post-vaccination	Day 92	92	65 to 147
180 days post-vaccination	Day 202	202	148 to 292
360 days post-vaccination	Day 382	382	≥293
Moderna vaccine:			
Pre-vaccination	Day 1	1	≤1
14 days post-vaccination	Day 43	43	(vaccine day + 1) to 71
70 days post-vaccination	Day 99	99	72 to 154
180 days post-vaccination	Day 209	209	155 to 299
360 days post-vaccination	Day 389	389	≥300

Note:

- Pre-vaccination and study day are derived as outlined in [Section 2.1.1](#).
- Vaccine day is the study day of the second dose of the COVID-19 vaccine.
- Assessments performed between the first and second doses of the COVID-19 vaccine are not assigned an analysis visit.

[figure not shown]

Table 5**Cohorts 2 and 3 visit windows for SARS-CoV-2 qualitative antibody / CD19+ B cells (Cohort 2 only) / T cell**

Analysis visit	Nominal time point	Scheduled visit day (target study day)	Visit window (study days)
Pfizer vaccine:			
Pre-vaccination	Day 1	1	≤1
14 days post-vaccination	Day 36	36	(vaccine day + 1) to 119
180 days post-vaccination	Day 202	202	120 to 247
270 days post-vaccination	Day 292	292	248 to 337
360 days post-vaccination	Day 382	382	≥338
Moderna vaccine:			
Pre-vaccination	Day 1	1	≤1
14 days post-vaccination	Day 43	43	(vaccine day + 1) to 126
180 days post-vaccination	Day 209	209	127 to 254
270 days post-vaccination	Day 299	299	255 to 344
360 days post-vaccination	Day 389	389	≥345

Note:

- Pre-vaccination and study day are derived as outlined in [Section 2.1.1](#).
- Vaccine day is the study day of the second dose of the COVID-19 vaccine.
- Assessments performed between the first and second doses of the COVID-19 vaccine are not assigned an analysis visit.

Table 6**Cohorts 2 and 3 visit windows for serum immunoglobulin (IgG, IgM)**

Analysis visit	Nominal time point	Scheduled visit day (target study day)	Visit window (study days)
Pfizer vaccine:			
Pre-vaccination	Day 1	1	≤1
180 days post-vaccination	Day 202	202	(vaccine day + 1) to 292
360 days post-vaccination	Day 382	382	≥293
Moderna vaccine:			
Pre-vaccination	Day 1	1	≤1
180 days post-vaccination	Day 209	209	(vaccine day + 1) to 299
360 days post-vaccination	Day 389	389	≥300

Note:

- Pre-vaccination and study day are derived as outlined in [Section 2.1.1](#).
- Vaccine day is the study day of the second dose of the COVID-19 vaccine.

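### The pooled primary response rates mix samples scheduled 14 days after dose 2 with samples taken at any later time, and the reference pool may include participants boosted before entry

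*SAP*

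**What the plan says.** **Timing of the primary sample.** SAP Section 1.1: "The primary analysis time point is Visit 4 for Cohorts 1, 2 and 3, and Visit 2 for Cohorts 4, 5 and 6". For Cohorts 1 to 3, Protocol Section 8 ties Visit 4 to the vaccine: "The Visit 4 lab samples should be collected 14 days after a participant has received their" second dose. For Cohorts 4 and 5, the inclusion criterion in Protocol Section 5.1 begins "Received two dose mRNA COVID-19 vaccine (Pfizer or Moderna vaccine" and requires only that at least 2 weeks have passed. No maximum is given. SAP Table 8 assigns any Cohort 4 or 5 sample from the day after dose 2 up to Study Day 1 to the 14-day post-vaccination visit.

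**Grouping.** SAP Section 2.1 lists "Cohorts 2 and 4 combined" as one reporting group and treats Cohorts 3 and 5 the same way. Protocol Section 12 agrees: "All summaries will be presented for Cohort 1, Cohorts 2 and 4, Cohorts 3 and 5, and Cohort 6". SAP Section 2.5.2 presents the primary endpoint by these groups and overall, and Section 2.2.1 plans no subgroup analysis.

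**Boosters.** The estimand (Protocol Section 2.1) defines Cohort 4 as not yet boosted and places boosted ofatumumab participants in Cohort 6. Cohort 5 participants, by contrast, "may or may not have received at least 1 COVID-19 mRNA booster". Table 8 counts from the booster in Cohort 6 but from dose 2 in Cohort 5, whether or not a booster followed.

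**Existing handling.** Protocol Section 12.5 says that participants enrolled after a booster, or boosted during the trial, will be analysed apart. SAP Section 2.5.6 repeats the primary analysis in Cohort 6 plus participants of Cohorts 1 to 5 boosted during the study. It does not name Cohort 5 participants boosted before entry. SAP Section 2.4.1 summarises time from MS therapy to first vaccine dose and to the primary time point, but not time from last vaccine dose to the primary sample.

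**The concern.** The clinical question is whether participants on ofatumumab mount a response. Whether a response lasts is a separate secondary objective. A Cohort 2 sample taken about 180 days after dose 2 feeds the secondary endpoint, while a Cohort 4 sample equally late feeds the primary one. The 2+4 rate therefore depends partly on how many participants came through each route and how long ago the Cohort 4 participants were vaccinated. The plan fixes neither.

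The two pools also differ in doses received. The protocol summary describes the purpose as a comparison with interferon or glatiramer acetate. If some reference participants have had a third dose and the 2+4 participants have not, part of any difference between the rows may reflect the booster. The planned tables would not let a reader separate response, waning and boosting.

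**Working it through.** **The plan's own figures.** Protocol Section 12.8.1 and SAP Section 3 give margins of 20.1, 19 and 17.5 points for n = 20 at rates of 70%, 75% and 80%. The normal approximation 1.96 × √(p(1−p)/20) gives 20.08, 18.98 and 17.53, so they reproduce. The exact intervals planned for the analysis are slightly wider: half-widths of 21.2 (14/20), 20.2 (15/20) and 19.0 (16/20).

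**What the documents leave open.** Each pool has 22 participants in combination. The 2:4 and 3:5 splits, the time since dose 2 in Cohorts 4 and 5, and the boosted share of Cohort 5 are not given. The calculations below rest on assumed values, apart from the 70–80% response rates, which are the plan's sample-size scenarios. They ignore missing data.

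**Waning.** Let p be the early response rate, w the share of the pool from the later-sampled cohort, and L the share of early positives who are negative by Visit 2.

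- Pooled rate = p − w·p·L.
- Low end: p = 70%, w = 0.25, L = 10% gives a fall of 0.25 × 0.70 × 0.10 = 1.75 points.
- High end: p = 80%, w = 0.75, L = 30% gives 0.75 × 0.80 × 0.30 = 18 points.
- Middle case: p = 80%, w = 0.5, L = 20% gives 8 points (80% to 72%).

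**Boosters in 3+5.** Let b be the boosted share of the pool and G the share of two-dose non-responders converted by the booster.

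- Gain = b·(1−p)·G.
- Low end: p = 80%, b = 0.25, G = 25% gives 0.25 × 0.20 × 0.25 = 1.25 points.
- High end: p = 70%, b = 0.75, G = 100% gives 0.75 × 0.30 × 1 = 22.5 points.
- Middle case: p = 80%, b = 0.5, G = 50% gives 5 points.

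**Effect on the contrast.** Suppose the true two-dose response is 80% in both groups. The two middle cases together, with waning in 2+4 only, give an apparent gap of 8 + 5 = 13 points. Waning in Cohort 5 would shrink it. With the same w and L in both pools and no boosters, both fall by 8 points and the gap is zero.

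**Precision of separate rows.** If the 20 evaluable participants split 10/10 (assumed), the exact half-width is 29.3 points at 7/10 and 26.5 at 8/10. With 15 in a cohort it is 24.9 (10/15) or 21.9 (12/15). With 5 it is 35.6 (4/5).

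**The case against.** The pooling is declared. Amendment 1 added vaccinated cohorts because US vaccination was declining, and enrolment targets are set for the combined groups. The endpoint is written as at least 14 days in Protocol Table 2-1, the estimand and the SAP, so a late sample is not a breach, although Protocol Section 12.4.1 says 14 days without the at-least. The analysis is estimation only. Response at about 180, 270 and 360 days is tabulated by group, and all data are listed. For the same participants, subtracting the mean times in SAP Section 2.4.1 yields the mean time from first vaccine dose to the primary sample. SAP Section 1 also cites protocol version 01, while the protocol in hand carries Amendment 2; the documents do not show whether version 01 contained the Section 12.5 sentence on boosters.

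Most of this stands, and it limits the point to one of interpretation. It does not supply a single-cohort estimate, the interval from last dose, or any handling of Cohort 5 participants boosted before entry.

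A reader might infer three stronger things that the documents do not support:

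- **That a negative in Cohort 2 shows no response was mounted.** The Pfizer window in SAP Table 5 reads "vaccine day + 1) to 119" (Moderna: 126). On the planned schedule it therefore runs to 119 − 22 = 97 days after dose 2 (126 − 29 = 97 for Moderna) and does not exclude samples before day 14. The worst categorical result in the window is taken, and missing assays count as non-response.
- **That waning penalises only ofatumumab.** Cohort 5 has the same open-ended interval, so 3+5 can fall too.
- **That response should be judged on Cohort 2 against Cohort 3.** That would re-target a pooled, estimation-only analysis, possibly on very few participants. With 4 in Cohort 2, for example, 3/4 has an exact 95% interval of about 19% to 99%.

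**Conclusion.** The point holds as a limit on interpretation. Each pooled primary proportion combines early response with positivity at an uncontrolled later time, and 3+5 may also include post-booster response. Waning can lower either pool. Under the estimand, a pre-entry booster can raise only the reference pool.

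The size cannot be computed from the documents. For response rates of 70–80%, waning lowers a pooled rate by 1.75 to 18 points if 25–75% of the pool is sampled late and 10–30% of early positives have reverted. Boosters raise 3+5 by 1.25 to 22.5 points if 25–75% of that pool is boosted and 25–100% of non-responders convert. The upper ends are about as large as the planned margin of 17.5 to 20.1 points, but they are illustrations. The net effect on the 2+4 versus 3+5 contrast depends on splits and intervals that the plan does not fix.

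**What to change.** - **SAP Section 2.5.2:** keep the pooled rows. Add descriptive primary-endpoint rows (n, %, exact 95% CI) for Cohorts 2, 3, 4 and 5 separately, with Cohort 5 split by booster status at Visit 2. Add a note that the Cohort 4 and 5 rows estimate positivity at the observed time since last dose.
- **SAP Section 2.5.6:** include Cohort 5 participants boosted before entry in the boosted analysis, to match Protocol Section 12.5.
- **SAP Section 2.4.1:** add time in days from last COVID-19 vaccine dose (dose 2 or booster) to the primary sample, by cohort.

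The cost is SAP text and a few table rows. The assessment schedules already put the Vaccine Administration Form in the database, and the SAP windows already need dose-2 dates and, for Cohort 6, booster dates. Cohort 5 booster dates are needed to check eligibility; confirm that they are in the database. The drawback is imprecision: half-widths of about 27 to 29 points at an assumed 10 per cohort, and wider in smaller cells. The new rows should be labelled descriptive.

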1.2 Study objectives, endpoints and estimands

Study objectives and associated endpoints are shown in Table 1.

Table 1 Study objectives and endpoints

Objective(s)	Endpoint(s)
Primary Objective(s) 
To assess immune response to non-live mRNA COVID-19 vaccine in ofatumumab-treated participants	Endpoint(s) for primary objective(s) 
Achieving immune response as defined by positive severe acute respiratory syndrome coronavirus 2 (SARS-CoV-2) qualitative Immunoglobulin G (IgG) antibody assay ≥ 14 days after full course (2 doses) vaccination (yes/no)
Secondary Objective(s) 
To assess sustained immune response to non-live mRNA COVID-19 vaccine in ofatumumab-treated participantsTo assess immune conversion to non-live mRNA COVID-19 vaccine in ofatumumab-treated participants	Endpoint(s) for secondary objective(s) 
Achieving immune response at other assessment time points (yes/no)Immune conversion to non-live mRNA COVID-19 vaccine (yes/no) defined as:
For participants with serum available prior to vaccination:
Pre-vaccination absence of SARS-CoV-2 spike IgG with post-vaccination SARS-CoV-2 positive qualitative antibody assay ≥ 14 days after full course (2 doses) vaccination (yes/no) orPre-vaccination serum presence of SARS-CoV-2 quantitative IgG antibody with post-vaccination ≥ 4-fold increase in SARS-CoV-2 quantitative antibody titer as determined by dilution assay ≥ 14 days after full course (2 doses) vaccination (yes/no)For participants with serum unavailable prior to vaccination and who have not received a booster (Cohorts 4 and 5):
Initial negative SARS-CoV-2 nucleocapsid antibody with post-vaccination SARS-CoV-2 positive qualitative antibody assay ≥ 14 days after full course (2 doses) vaccination (yes/no)

Objective(s)	Endpoint(s)

• To assess adverse events and serious adverse events	
• Adverse events/serious adverse events

1.2.1 Primary estimand(s)

The estimand is the precise description of the treatment effect and reflects strategies to address events occurring during the trial conduct which could impact the interpretation of the trial results (e.g., premature discontinuation of treatment).

The primary clinical question of interest is: Do relapsing MS participants who receive ofatumumab treatment mount an immune response to non-live mRNA COVID-19 vaccine?

The justification for the primary estimand is that it will capture whether ofatumumab-treated participants generate antibodies to mRNA COVID-19 vaccines.

The primary estimand is described by the following attributes:

- **Population:** Defined through appropriate inclusion/exclusion criteria to reflect the targeted population. Relapsing MS participants subdivided into 6 cohorts. (1) Will receive a full course (2 doses) of a COVID-19 mRNA vaccine \geq 2 weeks prior to starting ofatumumab 20 mg s.c. treatment; (2) Will receive a full course (2 doses) of a COVID-19 mRNA vaccine after \geq 4 weeks of commercial ofatumumab 20 mg s.c. treatment (3) Will receive a full course (2 doses) of a COVID-19 mRNA vaccine after \geq 4 weeks of interferon or glatiramer acetate treatment (4) Completed a full course (2 doses) of a COVID-19 mRNA vaccine after \geq 4 weeks of commercial ofatumumab 20 mg s.c. treatment but has not yet received a COVID-19 mRNA booster (5) Completed a full course (2 doses) of a COVID-19 mRNA vaccine after \geq 4 weeks of interferon or glatiramer acetate (may or may not have received a COVID-19 mRNA booster) (6) Completed a full course (2 doses) of a COVID-19 mRNA vaccine after \geq 4 weeks of commercial ofatumumab 20 mg s.c. treatment and received an additional booster vaccine \geq 14 days prior to screening
- **Variable:** Achieving immune response as defined by a positive SARS-CoV-2 qualitative IgG antibody assay \geq 14 days after full course (2 doses) vaccination (yes/no)

- **Treatment of interest:** Non-live COVID-19 mRNA vaccine either ≥ 2 weeks prior to ofatumumab start or ≥ 4 weeks after ofatumumab start or while on interferon or glatiramer acetate
- **Intercurrent event:** Discontinuation of treatment/study, or death
- **Summary measure:** Proportion of participants achieving immune response

